8. ADVERSE EVENT MONITORING AND REPORTING

The entities providing oversight of safety and compliance with the protocol require reporting as outlined below.

The Washington University Human Research Protection Office (HRPO) requires that all events meeting the definition of unanticipated problem or serious noncompliance be reported as outlined in Section 8.2.

There are minimal side effects associated with the NIR/US, therefore we will not be tracking AEs. All SAEs that occur within 24 hours of an NIR/US exam will be brought to the attention of the PI and a determination will be made if they are related or unrelated to study participation. Any SAE that is related to the NIR/US intervention, will be reported to the IRB.

8.1 Definitions

8.1.1 Adverse Events (AEs)

Definition: any unfavorable medical occurrence in a human subject including any abnormal sign, symptom, or disease.

Attribution (Relatedness), Expectedness, and Seriousness: the definitions for the terms listed that should be used are those provided by the Department of Health and Human Services' Office for Human Research Protections (OHRP). A copy of this guidance can be found on OHRP's website at: <http://www.hhs.gov/ohrp/policy/advevntguid.html>.

8.1.2 Serious Adverse Event (SAE)

Definition: any adverse drug experience occurring at any dose that results in any of the following outcomes:

- Death
- A life-threatening adverse drug experience
- Inpatient hospitalization or prolongation of existing hospitalization
- A persistent or significant disability/incapacity (i.e., a substantial disruption of a person's ability to conduct normal life functions)
- A congenital anomaly/birth defect
- Any other experience which, based upon appropriate medical judgment, may jeopardize the subject and may require medical or surgical intervention to prevent one of the outcomes listed above

8.1.3 Unexpected Adverse Experience

Definition: any adverse drug experience, the specificity or severity of which is not consistent with the current investigator brochure (or risk information, if an IB is not required or available).

8.1.4 Life-Threatening Adverse Experience

Definition: any adverse drug experience that places the subject (in the view of the investigator) at immediate risk of death from the reaction as it occurred, i.e., it does not include a reaction that, had it occurred in a more severe form, might have caused death.

8.1.5 Unanticipated Problems

- unexpected (in terms of nature, severity, or frequency) given (a) the research procedures that are described in the protocol-related documents, such as the IRB-approved research protocol and informed consent document; and (b) the characteristics of the subject population being studied;
- related or possibly related to participation in the research (in this guidance document, possibly related means there is a reasonable possibility that the incident, experience, or outcome may have been caused by the procedures involved in the research); and
- suggests that the research places subjects or others at a greater risk of harm (including physical, psychological, economic, or social harm) than was previously known or recognized.

8.1.6. Noncompliance

Definition: failure to follow any applicable regulation or institutional policies that govern human subject research or failure to follow the determinations of the IRB. Noncompliance may occur due to lack of knowledge or due to deliberate choice to ignore regulations, institutional policies, or determinations of the IRB.

8.1.7 Serious Noncompliance

Definition: noncompliance that materially increases risks, and results in substantial harm to subjects or others, or that materially compromises the rights or welfare of participants.

8.1.8 Protocol Exceptions

Definition: A planned deviation from the approved protocol that are under the research team's control. Exceptions apply only to a single participant or a singular situation. Pre-approval of all protocol exceptions must be obtained prior to the event.

8.2 Reporting to the Human Research Protection Office (HRPO)

The PI is required to promptly notify the IRB of the following events:

- Any unanticipated problems involving risks to participants or others which occur at WU, any BJH institution, or that impacts participants or the conduct of the study.
- Noncompliance with federal regulations or the requirements or determinations of the IRB.
- Receipt of new information that may impact the willingness of participants to participate or continue participation in the research study.

These events must be reported to the IRB within **10 working days** of the occurrence of the event or notification to the PI of the event. The death of a research participant that qualifies as a reportable event should be reported within **1 working day** of the occurrence of the event or notification to the PI of the event.

8.3 Reporting to the Quality Assurance and Safety Monitoring Committee (QASMC) at Washington University

The PI is required to notify the QASMC of any unanticipated problem occurring at WU or any BJH or SLCH institution that has been reported to and acknowledged by HRPO as reportable. (Unanticipated problems reported to HRPO and withdrawn during the review process need not be reported to QASMC.)

QASMC must be notified within **10 days** of receipt of IRB acknowledgment via email to a QASMC auditor.

8.4 Time Frame for Reporting Required Events

As noted above minimal adverse events are associated with NIR/US. If we are made aware of an AE/SAE then we will report this to the HRPO in the timeline noted in section 8.2.

9. DATA AND SAFETY MONITORING

In compliance with the Washington University Institutional Data and Safety Monitoring Plan, the Principal Investigator will provide a Data and Safety Monitoring (DSM) report to the Washington University Quality Assurance and Safety Monitoring Committee (QASMC) semi-annually beginning six months after accrual has opened (if at least five patients have been enrolled) or one year after accrual has opened (if fewer than five patients have been enrolled at the six-month mark). This report will include:

- HRPO protocol number, protocol title, Principal Investigator name, data coordinator name, regulatory coordinator name, and statistician
- Date of initial HRPO approval, date of most recent consent HRPO approval/revision, date of HRPO expiration, date of most recent QA audit, study status, and phase of study
- History of study including summary of substantive amendments; summary of accrual suspensions including start/stop dates and reason; and summary of protocol exceptions, error, or breach of confidentiality including start/stop dates and reason
- Study-wide target accrual and study-wide actual accrual

- Protocol activation date
- Average rate of accrual observed in month 1, month 2, and subsequent months
- Expected accrual end date
- Objectives of protocol with supporting data and list the number of participants who have met each objective
- Measures of efficacy
- Early stopping rules with supporting data and list the number of participants who have met the early stopping rules
- Summary of toxicities
- Abstract submissions/publications
- Summary of any recent literature that may affect the safety or ethics of the study

The study principal investigator and Research Patient Coordinator will monitor any potential issues on an ongoing basis. Once the principal investigator or Research Patient Coordinator becomes aware of an adverse event, the AE will be reported to the HRPO and QASMC according to institutional guidelines.

10. Statistical Considerations

10. 1 Study design.

The study consists of two phases. The training phase consists of 20 eligible participants as detailed in Section **“US-guided DOT database and Training”** to assess sources of variabilities. The formal phase is a prospective study to enroll up to 315 eligible participants who will undergo SOC biopsy and fall in the BIRAD categories of 3, 4A, 4B, 4C, or 5 to yield 300 with valid US-DOT data.

10. 2 Study hypotheses and endpoints.

Study Hypothesis 1 for aim 1.1: The first hypothesis is that the measured tHb distribution and values can be potentially used as an adjunct for radiologists to reduce unnecessary biopsies in low risk patients with benign pathological results. The benign biopsy spare rate can be calculated as $Gd/(Gb+Gd)$ in Fig.11, which is equivalent to the specificity, the primary endpoint of Aim1.1. We observed in previous studies that specificity could be improved by 45% on average if NIR data were used in the decision-making process. Note that the specificity in this group of biopsied patients under the SOC is 0% by definition. In this study, we conservatively set the minimum acceptable specificity at 30%. The null and alternative hypotheses, which demonstrate superiority when the NIR imaging data are used as an adjunct to the diagnostic assessment versus when the SOC diagnostic data are used alone, are given by

$$H_0: \text{Specificity} \leq 30\% \text{ versus } H_1: \text{Specificity} > 30\%$$

This aim will be considered a success if the lower limit of the 95% confidence interval on specificity exceeds 30%. This hypothesis will be tested at the one-sided 0.025 level, rather than 0.05, to account for the fact that two hypothesis tests (on specificity and sensitivity) are planned. This aim is considered a success if the lower limit of the 97.5% confidence interval on specificity exceeds 30%.

Study Hypothesis 2 for aim 1.2: The second hypothesis is that, while reducing unnecessary benign biopsies, the addition of adjunct information from US-DOT still maintains a high sensitivity

in capturing nearly all malignant tumors. This can be evaluated based on sensitivity, which is calculated as $G_a/(G_a+G_c)$, as shown in Fig.11.

H_0 : sensitivity $\leq 90\%$ versus H_1 : sensitivity $> 90\%$

Based on previous study, we anticipate the sensitivity will be in the range of 96-100%. This aim is considered a success if the lower limit of the 95% confidence interval for sensitivity is at least 90%. This hypothesis will be tested at the one-sided 0.025 level, rather than 0.05, to stringently account for the fact that two hypothesis tests (on specificity and sensitivity) are planned. This aim is considered a success if the lower limit of the 97.5% confidence interval for sensitivity is at least 90%.

10.3 Sample size justifications.

We expect ~300 eligible women who will undergo SOC biopsy with valid US-DOT data and fall in the BIRAD categories of 3, 4A, 4B, 4C, or 5, rendering ~210 pathologically benign biopsies and 90 malignant biopsies. **For Study Hypothesis 1**, prior study results indicate the specificity was estimated to be no less than 45%. A total of 83 benign biopsies are needed to achieve 80.18% power to test Study Hypothesis 1 at a 2.5% level. This calculation is based on a 1-sided exact binomial test by conservatively assuming the true specificity is 45%, while 210 benign biopsies achieve 99.4% power to test Hypothesis 1. We also calculated the sample size based on the more stringent requirement that the lower limit of the 1-sided 97.5% conservative Clopper-Pearson binomial exact confidence interval (CI) (60) to the estimated specificity (of 45%) should exceed 30%. The 210 benign biopsies will allow us to estimate the 1-sided 97.5% exact CI to be between 37.7%~100%, thus satisfying this more stringent requirement. **For Study Hypothesis 2**, 90 malignant biopsies will achieve 89.33% power to conduct Study Hypothesis 2 at a 1-sided 2.5% level, based on a 1-sided exact binomial test. With 90 malignant biopsies, the sensitivity can be estimated at 98% with a 1-sided 97.5% exact CI of 92.06%~100%, thus satisfying the stringent criterion requiring a lower limit of >90%.

In calendar year 2016, over 7,000 women came to the Siteman Cancer Center at WashU for diagnostic evaluation. Approximately 17% had suspicious or highly suggestive malignancy findings and were recommended for tissue sampling. Over 700 women underwent US guided biopsy, which is more than 10 times larger than the potential study subjects each year.

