2 OBJECTIVES

We have received 5-year NCI funding to support this study.

The primary objective of this study is to assess the ability of US-guided DOT to reduce the rate of benign biopsy. To achieve this objective we will simultaneously acquire co-registered US imaging data and US-guided DOT imaging data from a group of patients (~300) scheduled for US-guided breast biopsy. We hypothesize that the additional optical information of tHb concentration and distribution will lead to a downgrading of the assessment of a subset of low to moderate suspicion

abnormalities based on conventional imaging (i.e. breast ultrasound with or without mammography) and thereby could lead to a reduction in benign breast biopsies (i.e. false positives).

The secondary and complementary objective is to assess the impact on sensitivity of adjunctive optical data. In particular we hypothesize that by defining a conservative tHb threshold below which malignancy is so rare that the addition of US-guided DOT will not significantly alter the sensitivity of the combined US-guided DOT & CI assessment, i.e. adjunctive US-guided DOT will not decrease true positives.

A third objective is to assess the impact of adjunctive US-guided DOT data in the management of discordant pathology results. In current SOC, the radiologist performing the needle biopsy routinely compares the imaging with the pathology results for concordance. Highly suspicious abnormalities (BI-RAD 4C, 5) that yield benign results are typically considered discordant and are recommended for repeat biopsy or surgical excision. If the discordant abnormality has a tHb below the minimum threshold value, this might allow radiologists to forego a repeat biopsy or surgery. For example, focal fibrosis may appear highly suspicious on US. Our initial data show that fibrotic lesions have low vascularity (28).

Additionally as an exploratory objective, we will compare the results of US-guided DOT and in particular tHb concentration with contrast enhanced mammography (CEM) in the subset of patients who undergo CEM.

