To accomplish the aims of assessing the impact of adjunctive US-guided DOT on reducing benign biopsy recommendation (i.e. FPs), while maintaining sensitivity (i.e. TPs) we will conduct a reader study of the 300 subject trial. Three of four study radiologists will serve as study readers for each case. (To eliminate potential bias a study radiologist performing the biopsy will not serve as a reader for that case.) As noted above the study radiologist who performs or supervises the US-guided DOT exam will be one of the readers. Two additional study radiologist readers will subsequently and independently review the available pre-existing patient information and CI data, (excluding the US-guided biopsy exam) and complete CI and DOT CRFs blinded to the pathology result of the abnormality that underwent biopsy. The CRFs include a BI-RADS assessment. The reader will first complete the CI CRF blinded to the US-guided DOT result, then after reviewing the optical data (tHB concentration and distribution) the reader will complete the DOT CRF including the impact of US-guided DOT information on the BI-RADS assessment, i.e. no change, decreased or increased.

Similar to the CI plus DOT workflow, for cases that have CEM, a CI CRF will be completed first, followed by a CEM specific CRF including a BI-RADS assessment and the impact of CEM on the BI-RADS assessment will be recorded. As noted above, the study radiologist that supervises the US-guided DOT and CEM exams will serve as one of the study readers. For the subsequent two readers we will alternate which adjunctive modality (i.e. CEM or US-DOT) is reviewed first and separate the subsequent review of the second adjunctive modality by a minimum of 4 weeks to prevent recollection bias).

Figure 4 diagrams the core analysis. Combined CI and US-guided DOT BI-RADS 2 and 3 assessments will be considered test negative, and BI-RADS 4A, 4B, 4C, and 5 assessments will be considered test positive. For negative tests, the biopsy proven malignant group (Gc, see Fig. 1(b)) represents false negative results, and the benign group Gd represents true negatives and reflects the potential reduction in benign biopsy recommendation if US-guided DOT were used as SOC. Ga represent true positives and Gb represent false positives utilizing adjunctive US-guided DOT. A comparison of the Ga groups i.e. CI alone vs. CI & DOT will constitute the assessment of the effect of adjunctive US-guided DOT on sensitivity.

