10.4 Data Analysis

All data will be analyzed as it is without imputations. Summary statistics will be used to summarize data including mean, median, standard deviation, interquartile range for continuous data and count (percentage) for categorical data.

All evaluable subjects will be analyzed. In addition to the specificity and sensitivity of US-guided DOT results, PPV, NPV, and overall accuracy will be calculated. The two study hypotheses will be tested by a binomial exact test and by constructing the one-sided 97.5% Clopper-Pearson exact confidence intervals for specificity and sensitivity. The lower limit will determine the achievement of study goals. We will explore the data further to refine the classification algorithm and the cut-off threshold. ROC analysis will evaluate the quantitatively measured tHb for pathological results of malignant biopsies. Besides tHb and its distribution, other parameters (such as oxyHb, deoxyHb, and distributions) will be either linearly incorporated with tHb to maximize the ultimate area under ROC or non-linearly through a tree-based classification model (e.g., using the R package “rpart”) (62).

The area under the ROC will be calculated to gauge the model's overall discriminative ability for biopsy results.

For the exploratory study (discordant biopsy results), the imaging data (e.g., tHb, oxyHb etc) will be summarized as appropriate in the subset of participants whose BIRAD results yield highly suspicious abnormalities (BI-RAD 4C, 5) but pathology yield benign results. Two sample t-test or Wilcoxon rank sum test as appropriate will be applied to compare this subset versus those with a malignant biopsy.

For the exploratory Study (CEM DOT correlation), we will compare BI-RADS assessments of CI&CEM vs. CI&US-guided DOT as well as correlate imaging data such as intensity of enhancement in CEM and the total hemoglobin level of US-DOT using Pearson or Spearman correlation coefficients. We will evaluate concordance/disconcordance between US-guided DOT and CEM using agreement measure (Kappa coefficient) and will test the discordance using McNemar test.

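### Aim 1.2 is decided by testing combined sensitivity against a fixed 90%, which cannot show that DOT leaves true positives undiminished compared with conventional imaging alone

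*Combined protocol and SAP*

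**What the plan says.** **The question is comparative.** Section 2 gives the secondary objective as an effect on sensitivity and glosses it as: "adjunctive US-guided DOT will not decrease true positives". Section 7 has each reader complete a CI form blinded to DOT, then a DOT form recording whether the BI-RADS assessment changed. It then names the analysis: "A comparison of the Ga groups i.e. CI alone vs. CI & DOT will constitute the assessment of the effect" (that is, what DOT does to sensitivity).

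**The decision rule is not.** Section 10.2 defines sensitivity as Ga/(Ga+Gc) for the combined read and tests a null of 90% or less. It states the success rule twice, first as "This aim is considered a success if the lower limit of the 95% confidence interval for sensitivity is at least 90" per cent, then as "This aim is considered a success if the lower limit of the 97.5% confidence interval for sensitivity is at least 90" per cent. Section 10.4 confirms the method: "The two study hypotheses will be tested by a binomial exact test and by constructing the one-sided 97.5% Clopper-Pearson exact confidence intervals". This covers both endpoints, with the lower limit determining whether the study goals are met. No statistic, interval or decision role is given for CI alone versus CI and DOT. The only paired test named is McNemar's, for DOT versus contrast-enhanced mammography.

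**The cohort.** Section 7.1 (Aim 1.1) treats all subjects, apart from a few BI-RADS 3 cases tracked separately, as positive under standard of care because they were recommended for biopsy. It concludes that standard-of-care specificity is 0%. It does not draw the matching conclusion that standard-of-care sensitivity is about 100%.

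**The concern.** The test that decides Aim 1.2 has no CI-alone term, so it does not measure the effect that section 7 says will be assessed. Two things follow.

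First, if nearly every cancer in the cohort is positive under standard of care, a sensitivity above 90% is compatible with losing almost 10% of them. The plan neither names nor justifies that tolerance.

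Second, the combined figure merges two sources of negative calls. Readers make their own CI assessment and may call a cancer BI-RADS 2 or 3 before seeing any DOT data; such a case counts as a miss for the combined read unless DOT upgrades it. DOT may also raise an assessment, so upgrades can hide downgrades. A pass or a fail could therefore reflect the readers' CI calls and not DOT. For a tool meant to spare biopsies, missed cancers are the main risk, so the claim about them should rest on the comparison that isolates DOT.

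**Working it through.** **Inputs.** 90 malignant biopsies among about 300 (section 10.3); null 90%, one-sided 0.025 (section 10.2); exact binomial test and Clopper-Pearson limit (section 10.4); anticipated sensitivity 96–100% (section 10.2). The power sentence does not state its alternative; 98% is inferred from the sentence that follows it. Each cancer is taken to give one result, although three readers read each case.

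**Step 1: reproduce the plan's figure.** The smallest r with P(X ≥ r | n = 90, p = 0.90) ≤ 0.025 is r = 87, with exact size 0.0169. Power at 98% is P(X ≥ 87 | 90, 0.98) = 0.8933, matching the stated 89.33%.

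**Step 2: what passes.** The lower limit L for x of 90 solves P(X ≥ x | 90, L) = 0.025.
- 87/90 = 96.7%: L = 90.6%, pass. The upper limit on loss is 100 − 90.57 = 9.43%.
- 86/90 = 95.6%: L = 89.0%, fail.

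So up to 3 of 90 cancers may be called BI-RADS 2 or 3. The two success sentences agree only if the 95% interval is two-sided and the 97.5% interval one-sided. If the 95% interval were one-sided, 86/90 would give 90.1% and 4 misses would pass.

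**Step 3: chance of success by true combined sensitivity**, P(X ≥ 87 | 90, p):

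| True sensitivity | 90% | 94% | 95% | 96% | 97% | 98% |
|---|---|---|---|---|---|---|
| P(success) | 0.017 | 0.20 | 0.34 | 0.51 | 0.72 | 0.89 |

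**Step 4: what the rule cannot distinguish.** Constructed examples with 90 cancers:

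| Example | CI alone positive | DOT: positive to negative | DOT: negative to positive | CI and DOT positive | Rule | Net change due to DOT |
|---|---|---|---|---|---|---|
| A | 90 | 3 | 0 | 87 | pass | −3/90 = −3.3 points |
| B | 87 | 0 | 0 | 87 | pass | 0 |
| C | 87 | 3 | 3 | 87 | pass | 0, with 3 downgrades hidden |
| D | 86 | 0 | 0 | 86 | fail | 0 |

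A, B and C give the same test result with quite different DOT effects. D fails although DOT changed nothing. Only the paired table separates them.

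**Step 5: precision of a paired analysis.** With zero losses in n cancers the 97.5% upper limit on loss is 1 − 0.025^(1/n).
- n = 90: 4.0%.
- Per reader, if reads are balanced (an assumption), n = 90 × 3/4 = 67.5, about 68: 5.3%.

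A formal margin would be hard to meet. Suppose CI alone is positive for all 90 and DOT only removes positives. With an assumed 5-point margin, one loss already gives an upper limit of 6.0%, so only zero losses pass. Power is then 0.99^90 = 0.40 at a true loss of 1% and 0.98^90 = 0.16 at 2%. McNemar's test is no safeguard either: 3 losses and no gains give a two-sided p of 2 × 0.5³ = 0.25.

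**The case against.** The strongest reply is that the standard-of-care comparator is built in. If referral makes sensitivity about 100%, one minus the combined sensitivity is the loss against referral, and testing against 90% is in effect a 10-point margin. The plan uses the same fixed-reference reasoning openly for specificity. Aim 1.2 and Hypothesis 2 also speak of keeping sensitivity high, and the section 2 sentence allows for no significant alteration, so 90% can be a legitimate performance goal. All of that stands, and it is why the test should be kept. It does not cover the comparison with the readers' own CI-alone assessments, which is the one section 7 names.

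It can also be said that section 7 remains current text, that the forms capture movement in both directions, and that section 7.1 plans an ad hoc look at false negatives. This is true of data capture. But no analysis is specified for the comparison, and section 10.4 gives the decision to another test.

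Some stronger inferences are not supported:
- *The rule is lenient because it passes 51% of the time at 96%.* That value lies in the plan's anticipated range, so the figure shows limited power there; false success at 90% is 1.7%.
- *Participants' cancers will go unbiopsied because of DOT.* DOT is performed before biopsy in patients already referred, and its effect on recommendations is assessed in a reader study. Losses are hypothetical.
- *The plan commits to reporting a pass as no decrease.* It contains no such statement; the risk lies in the wording of the objective.

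**Conclusion.** The concern holds as a mismatch between the comparative question in sections 2 and 7 and the single-arm decision rule in sections 10.2 and 10.4. A pass establishes that combined sensitivity exceeds 90%. It does not establish that true positives were not decreased, and it cannot attribute misses to DOT.

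Against biopsy referral the unstated tolerance is about 10 points: up to 3 of 90 cancers, with an upper limit on loss of 9.4%. This rests on 90 cancers, one result per cancer, standard-of-care sensitivity of about 100%, and the one-sided 97.5% limit. Those figures measure loss against referral only. The size of the CI-alone problem cannot be estimated from the documents, which give no CI-alone reader sensitivity; the examples in step 4 show that it can act in either direction.

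A reader might infer that the planned test is invalid or its power wrong. Neither follows: the power reproduces, and the test suits the narrower claim.

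**What to change.** 1. In section 10.2, keep the 90% test as a performance goal and state that success means *sensitivity exceeds 90%*. Reconcile the 95% and 97.5% sentences by giving the sidedness of each interval.
2. In section 10.4, specify the comparison that section 7 promises. Among malignant lesions, cross-tabulate CI-alone positive/negative by CI and DOT positive/negative. Report positive-to-negative and negative-to-positive moves separately, and give the paired difference in sensitivity with a 95% confidence interval. Do this per reader and pooled over the three reads per case, with a pooled interval that allows for clustering by case and reader.
3. Report alongside it the loss against the standard-of-care biopsy referral.
4. Present items 2 and 3 as estimation, with no new pass/fail margin, and acknowledge the limited precision shown in step 5.

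No new patients, procedures or forms are needed. The cost is SAP wording, one more analysis table, and a more modest claim for Aim 1.2.
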